In 2014, a change of protocol was approved that extended the study treatment to 21 days. Patients will start the study medication 2 weeks prior to their surgery date and continue for the 1 week duration of the stent. Patients in the monotherapy arm will be given a set of Tamsulosin and placebo pills, while the combination therapy arm will be given a set of Tamsulosin and Tolderodine ER, with sufficient quantities for 21 days. Pill counts will be obtained at the end of the follow-up period to ensure compliance. All patients enrolled into the study will complete the USSQ at baseline prior to starting medication to serve as a baseline assessment of urinary symptoms, prior to stent insertion, and again at 24 hours, 5 days after stent insertion and post stent removal. The patients will have the stent removed in 7 days, which will conclude the study period. If the stent needs to be removed sooner, it will be arranged as per current protocol. Early termination is only relevant if the 5 day USSQ is not completed. In the 21-day regimen, 106 patients are planned to be enrolled. Thus, a total of 201 patients, to see if there is a difference with the longer duration of medication treatment. Subjects have been enrolled on this 21-day regimen since 10/29/2014, and all new subjects use this regimen.

STUDY POPULATION

The key participants of this study will be male and female adult patients with kidney or ureteral stones, or other conditions, requiring unilateral or bilateral ureteral stent placement, either before or after a surgical intervention. Specifically, the post-operative

University of Wisconsin-Madison

Study #: 2017-0755

IRB Approval Date: 7/17/2017

stent patients will include those who have undergone ureteroscopy, percutaneous nephrolithomy or extracorporeal shock-wave lithotripsy.

INCLUSION CRITERIA

Patients with unilateral or bilateral ureteral stent placement for urolithiasis are candidates for enrollment. These include: patients who have undergone ureteroscopy for renal or ureteral calculi, percutaneous nephrolithotomy (PCNL), shock-wave lithotripsy (SWL), or other conditions requiring stent placement post operatively, or for relief of pain or obstruction.

EXCLUSION CRITERIA

Candidates will be excluded from the study if ANY of the following apply:

1. Pre-existing LUTS
2. Active UTI
3. Contraindication to anticholinergic medication
 - a. Prior hypersensitivity or allergy to tolterodine

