Regular inquiries of study flow, pertaining to patient recruitment, randomization, patient compliance (with medication and completing questionnaires) and adverse events will be scheduled to occur after the first week and subsequently every two weeks during the active patient enlistment phase. Any adverse events/side effects will be monitored as per

University of Wisconsin-Madison

Study #: 2017-0755

IRB Approval Date: 7/17/2017

standard protocol in clinical use. Patients will be instructed to report any untoward reactions to the study drugs to the urology clinic or on-call urology staff.

No significant adverse events are anticipated with either of the study drugs, as they are routinely used in everyday urology practice. The patient will report side effects if and when they occur; the drug will be stopped if continuation is deemed inappropriate. Any adverse events or unanticipated problems will be recorded and the offending drug will be stopped, and the patient counseled accordingly. If a patient has side effects that precludes their ongoing participation in the study, they will be withdrawn and considered a study drop-out. All measures will be in effect to prevent breaches of confidentiality and/or emotional upset.

Patients are instructed to contact their treating surgeon if they have symptoms that may require placing the stent or having surgery sooner than expected. The surgeons who perform these procedures are also members of the study team, and will ensure that all patients' clinical care will not be influenced due to study participation. We confirm that study participation will not delay needed clinical care in the event that an enrolled subject requires stent placement sooner than anticipated. We will only include patients whose stent placement will not be delayed as a result of study participation. If the patient has the stent placed in the interim or has discontinued medications, he or she will be excluded from the study.

University of Wisconsin-Madison

Study #: 2017-0755

IRB Approval Date: 7/17/2017

STATISTICAL ANALYSIS & POWER CALCULATIONS:

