In 2014, a change of protocol was approved that extended the study treatment to 21 days. Our sample size calculation in the 21-day regimen was based on the recommended sample size calculations by the original developers of the USSQ ¹. The authors' calculations were based on the results of their validation studies that compared mean domain score and standard deviation differences between stented and control patients, using a 2-tailed test ($p < 0.05$). The percentage change (15%) translates to an absolute change in score by 4 points. Additionally, we extrapolated data from a recent meta-analysis evaluating the efficacy of tamsulosin to relieve stent related symptoms, which showed a mean standard deviation of 6.5 points between the tamsulosin and placebo arm ⁴ to confirm the previous authors' sample size. With an expected decrease of 4 points with the combination therapy, and an assumption of similar standard deviation (6.5), a two-tailed t-test ($p = 0.05$) and power of 0.80, our calculation yielded 43 patients per arm. Given the relatively similar numbers from the two calculations, we opted to use the more conservative sample size of 53 patients per arm as the data collection endpoint.

We are assessing for both an absolute and relative change in the USSQ scores.

1. We will be assessing for a relative change of 4 actual points (which translates to a 15% change, as per Joshi et al's validation study) within each group from immediately post stent insertion at 24 hours compared to day 5.
2. We will also assess for a change in scores between groups, i.e. comparing the mean intra-group score change as described in 1 (i.e., immediately post stent insertion at 24 hours compared to day 5).

University of Wisconsin-Madison
Study #: 2017-0755
IRB Approval Date: 7/17/2017

The questionnaire responses will be analyzed using cross tabulations and descriptive statistics to assess differences between groups. Paired *t*-tests will be used to assess within-group change in scores from the USSQ (comparison between post-op, i.e. at 48 hours, and day 5) and other discriminant properties. *T*-tests will be used to assess inter-group score changes.

The intent-to-treat principle will be employed in the event subjects have to withdraw from their assigned group, although this is not expected given that both treatment medications are used extensively in urology, and both treatment regimens are occasionally employed based on anecdotal physician experience.

DATA SECURITY:

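### Excluding randomised patients who stop study drug leaves them without outcome scores, so the promised intent-to-treat analysis cannot be carried out for them

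*Combined protocol and SAP*

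**What the plan says.** Patients are randomised after consent and history (Patient Screening and Recruitment). On the current regimen, "Patients will start the study medication 2 weeks prior to their surgery date and continue for the 1 week duration of the stent" (Study Activities). That puts 14 of the 21 drug days before the stent.

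Safety and Monitoring has two rules for patients who stop:

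- "If the patient has the stent placed in the interim or has discontinued medications, he or she will be excluded from the study". This closes a paragraph about patients who need a stent sooner than planned.
- "If a patient has side effects that precludes their ongoing participation in the study, they will be withdrawn and considered a study drop-out".

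Statistical Analysis & Power Calculations says: "The intent-to-treat principle will be employed in the event subjects have to withdraw from their assigned group, although this is not expected". It compares the arms on each patient's change in USSQ score from 24 hours to day 5 after insertion. (A later sentence in that section gives 48 hours for the first time point; this point is unaffected.)

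Two statements in Study Activities bear on follow-up: "All patients enrolled into the study will complete the USSQ at baseline prior to starting medication", with later questionnaires before insertion, at 24 hours, at day 5 and after removal; and "Early termination is only relevant if the 5 day USSQ is not completed", which follows a sentence on early stent removal.

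On numbers, "In the 21-day regimen, 106 patients are planned to be enrolled", and in the statistical section "we opted to use the more conservative sample size of 53 patients per arm as the data collection endpoint".

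The document does not define an analysis set, say whether questionnaires continue after a drug stop, or give a method for missing scores.

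**The concern.** Stopping drug is a post-randomisation event and may be related to treatment. Both arms take tamsulosin, but only the combination arm takes tolterodine. Its listed side effects include dry mouth, constipation and acute urinary retention, the last of which is close to the outcome being measured. Safety and Monitoring also directs that the responsible drug be stopped after an adverse event. Read with the exclusion sentence, a side effect can lead to a drug stop and then to removal from the study.

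A patient removed before the stent is unlikely to have a 24-hour or a day-5 score, and analysing by assigned arm does not supply one. What is at stake is whether the groups compared are still the groups randomised. Lost scores cannot be recovered at the analysis stage, and replacing excluded patients would restore numbers without removing a bias.

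The plan does not expect withdrawal, yet Study Activities reports 15 of 95 patients withdrawn on the 7-day regimen. Arms and reasons are not given, so this shows that attrition occurs, not that drug stops caused it.

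**Working it through.** **Inputs from the document.** Target difference 4 points, SD 6.5, two-sided 0.05, power 0.80, 43 per arm calculated and 53 per arm adopted (Statistical Analysis & Power Calculations); 106 planned and 15 of 95 withdrawn on the 7-day regimen (Study Activities).

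**Inputs assumed.** The split of losses between arms; a gap of 2 to 4 points between excluded and retained patients, taken as the same in both arms; and SD 6.5 for the change score. The gap must be in the 24-hour to day-5 *change*. Patients who score higher or lower by the same amount at both visits cause no bias, because the difference cancels.

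**1. The plan's own figure.** Two-sample t-test, noncentrality = 4 / (6.5 × √(2/n)). The solution is n = 42.43, rounded up to 43 per arm, so the stated figure reproduces. At 53 per arm the noncentrality is 4/1.263 = 3.17 and power is 0.881.

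**2. Scale of loss.** 15/95 = 15.8%; 0.158 × 106 ≈ 17 patients. Planned enrolment is 2 × 53 = 106, so there is no explicit allowance for losses beyond the margin of 53 over 43.

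**3. Shift in the between-arm difference.** In each arm the retained mean differs from the full mean by (excluded/53) × gap. With the same gap in both arms, equal losses cancel:

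shift = (excess exclusions in the combination arm / 53) × gap

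- 3 excess: 3/53 × 2 = 0.11; 3/53 × 4 = 0.23 points
- 8 excess: 8/53 × 2 = 0.30; 8/53 × 4 = 0.60 points

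**4. False-positive rate.** Noncentral t with noncentrality = shift / (6.5 × √(1/n₁ + 1/n₂)).

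| Excluded (combination, control) | Remaining | Shift | Noncentrality | False-positive rate |
|---|---|---|---|---|
| 10, 7 | 43 vs 46 | 0.11 | 0.11/1.379 = 0.08 | 5.1% |
| 10, 7 | 43 vs 46 | 0.23 | 0.23/1.379 = 0.16 | 5.3% |
| 12, 4 | 41 vs 49 | 0.30 | 0.30/1.376 = 0.22 | 5.5% |
| 12, 4 | 41 vs 49 | 0.60 | 0.60/1.376 = 0.44 | 7.2% |
| 8, 0 | 45 vs 53 | 0.60 | 0.60/1.318 = 0.46 | 7.4% |

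**5. Power for 4 points, from lost numbers alone.**

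| Remaining | Power |
|---|---|
| 53 vs 53 | 0.88 |
| 45 vs 45 | 0.82 |
| 43 vs 46 | 0.82 |
| 41 vs 49 | 0.82 |
| 37 vs 45 | 0.78 |

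The last row needs 24 of 106 lost (23%), above the only observed rate.

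**6. Power if the shift also hides part of a true effect.** At 43 vs 46, an effect of 4 − 0.11 = 3.89 gives 0.80, and 4 − 0.23 = 3.77 gives 0.77. In the extreme case, 41 vs 49 with 4 − 0.60 = 3.40, power is 0.685.

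**The case against.** **The sentence may be narrower than it looks.** It ends a paragraph about early stent placement, sits in a safety section, and may mean only that participation ends, with the statistical section governing analysis. A reader might infer that the plan definitely discards stopped patients and flatly contradicts itself; the documents do not go that far. Continued follow-up is unclear, not ruled out. But the wording is not limited to early stenting, the narrow reading still covers 14 of 21 drug days, and an intent-to-treat statement does not create a score for someone who left before the stent. The sentence on early termination does not settle it either, since it follows a remark on early stent removal.

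**Unequal stopping is inferred.** It rests on a list of side effects. Tamsulosin has its own list and is taken in both arms, and blinding limits arm-aware decisions. That stands: the imbalance is plausible and not shown. Blinding does not, however, prevent a drug's own side effects from driving stops.

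**The outcome is a change over about four days.** A level difference between excluded and retained patients cancels. That stands too, and it limits the harm. A gap of 4 points in change equals the whole target effect, and nothing in the documents supports one that large.

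**Power is adequate.** At the only observed withdrawal rate it stays near 0.82, above the planned 0.80. A reader might infer that the trial is underpowered; the figures do not support that.

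**Conclusion.** The point holds as a fault in a stated rule. Following the two Safety and Monitoring sentences as written would defeat the intent-to-treat analysis for patients who stop drug, above all before the stent. It should be changed, mainly because missing scores cannot be restored later.

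The numerical effect is unknown in size and direction. Under a moderate assumption (3 excess exclusions, a 2 to 4 point gap in change scores) it is small: a shift of 0.11 to 0.23 points, or 3% to 6% of the 4-point target. The 0.60-point shift (15% of target), the false-positive rate of about 7% and the power of 0.685 need both a lopsided loss and the largest assumed gap. They mark an outer case, not an expectation. The 15.8% anchor comes from a regimen with no two-week pre-stent period and is not a drug-stop rate.

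The first sentence also excludes patients stented early. That too is after randomisation, but the documents give no reason to expect it to differ by arm, so the conclusion rests on drug stops.

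**What to change.** 1. In Safety and Monitoring, delete discontinuing medication as a ground for exclusion. Amend the separate drop-out sentence as well, since it governs side-effect stops: stopping for side effects should end study drug only, and follow-up should continue unless consent is withdrawn. The clinical grounds for stopping a drug stay as they are.
2. Collect the 24-hour and day-5 USSQ, timed from the actual stent insertion, from every randomised, stented patient who has not withdrawn consent, including those stented early.
3. In the statistical section, state that the between-group comparison uses all randomised, stented patients by assigned arm. Report drug stops and missing scores by arm, and add a simple sensitivity analysis for missing change scores, for example assuming values 2 to 4 points better or worse than those observed. Show separately the patients handled under the present wording.

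The required sample size does not change. The cost is a short amendment, data fields for the date and reason of stopping, and slightly more follow-up. The estimate will include some patients off drug or with less than two weeks of pre-treatment, which is what intent-to-treat implies. Scores already lost since the 21-day regimen opened on 10/29/2014 may not be recoverable.

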Patients who will be undergoing urinary stent insertion during the management of renal or ureteral stones, or other conditions requiring endoscopy will be randomized into the combination or monotherapy arm, based on a computer generated randomization scheme, and will be enrolled into the study arm in a blinded manner. The study is intended to be double-blinded. The drug kit will be linked to the randomization number and both the investigator and patient will thus be blinded to the treatment. All patients will be required to provide a signed informed consent, which outlines the differences in the two treatment arms and study objectives. Patients will be provided the corresponding pills in pre-filled vials, based on their group assignment. Initially, the study used a 7-day treatment regimen. Patients in the monotherapy arm were given a set of Tamsulosin and placebo pills, while the combination therapy arm were given a set of Tamsulosin and Tolderodine ER, with sufficient quantities for 7 days. Pill counts were obtained at the end of the follow-up period to ensure compliance. All patients enrolled into the study were asked to complete the USSQ prior to stent insertion to serve as a baseline assessment of urinary symptoms, and again at 24 hours, 5 days after stent insertion and post stent removal. In the 7-day regimen, 80 patients were enrolled and completed the study (15 patients enrolled but withdrawn, 95 patients in total).

University of Wisconsin-Madison

Study #: 2017-0755

IRB Approval Date: 7/17/2017

The data analysis shows no benefit from being on combination therapy likely secondary to the short duration of therapy.

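### The only between-arm test listed measures change from 24 hours after stenting, when study drug has already run for two weeks, so any benefit present by then is subtracted out

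*Combined protocol and SAP*

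**What the plan says.** **Timing of drug and scores.** For the 21-day regimen, STUDY ACTIVITIES states: "Patients will start the study medication 2 weeks prior to their surgery date". The USSQ is completed before medication, before stent insertion, at 24 hours and 5 days after insertion, and after stent removal.

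**Objective.** OBJECTIVES AND HYPOTHESIS bases the objective on the mean difference in the urinary symptom index. It also hypothesises greater relief when tolterodine ER is started two weeks before the stent.

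**Between-arm test.** STATISTICAL ANALYSIS & POWER CALCULATIONS, item 2, defines the group comparison as "comparing the mean intra-group score change as described in 1", that is, the change from 24 hours to day 5. T-tests are assigned to these inter-group changes. A later sentence on the paired tests starts the change at 48 hours instead. The section also plans cross tabulations and descriptive statistics by group.

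**Numbers.** The power calculation uses 4 points, SD 6.5, a two-tailed 0.05 test and power 0.80, and gives 43 per arm. The plan then says "we opted to use the more conservative sample size of 53 patients per arm as the data collection endpoint". STUDY ACTIVITIES says "In the 21-day regimen, 106 patients are planned to be enrolled". For the 7-day phase it reports "80 patients were enrolled and completed the study (15 patients enrolled but withdrawn, 95 patients in total". On withdrawal from the assigned group, the statistical section says "although this is not expected given that both treatment medications are used extensively in urology".

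**The concern.** The 24-hour score was a natural reference under the 7-day regimen. Under the 21-day regimen it is taken after about 15 days of study drug (14 before surgery plus 1). A t-test on change from that point credits the combination only with what it gains over the next four days.

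The plan's own rationale suggests that this matters. BACKGROUND AND SIGNIFICANCE cites a study in which tolterodine ER did not differ from placebo at 1 week but did by week 4. STUDY ACTIVITIES puts the absence of benefit in the 7-day phase down to short treatment. If the lead-in works as intended, part of the benefit should be visible at 24 hours, where the planned test removes it. A real day-5 difference could then be reported as no difference.

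Two smaller matters sit beside this. The analysed change has two starting times, and the plan does not say whether 4 points and 6.5 describe a score or a change. Also, 53 per arm with data cannot be reached from 106 enrolled if anyone is lost.

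**Working it through.** **Inputs from the plan:** difference 4, SD 6.5, two-sided 0.05, power 0.80, 53 per arm, 106 enrolled, 15 of 95 withdrawn in the 7-day phase. **Not in the plan:** the fraction f of the effect present at 24 hours, the within-patient correlation ρ, and loss in the 21-day regimen. These are shown as ranges or labelled assumptions.

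**1. The plan's figure.** Normal approximation: n = 2 × (6.5/4)² × (1.960 + 0.842)² = 41.5, so 42. The t-based solution is 42.43, so 43 per arm. The figure reproduces. All power below is from the two-sample t-test (noncentral t). At 53 per arm it is 0.881.

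**2. What the change test estimates.** Let D24 and D5 be the arm differences in score at 24 hours and day 5. The difference in change is D5 − D24. If D24 = f × D5 and D5 = 4, the tested difference is 4(1 − f). Assume also that 6.5 is the SD of the change. The second power column, 44.63 per arm, is derived in step 4.

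| f at 24 hours | tested difference | power, 53 per arm | power, 44.63 per arm |
|---|---|---|---|
| 0 | 4.0 | 0.881 | 0.820 |
| 10% | 3.6 | 0.806 | 0.735 |
| 25% | 3.0 | 0.653 | 0.578 |
| 50% | 2.0 | 0.348 | 0.301 |

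The smallest difference giving 0.80 at 53 per arm is 3.571 points, so f may be at most 1 − 3.571/4 = 10.7%, or 0.43 points. At 44.63 per arm it is 3.898 points, so f may be at most 2.5%, or 0.10 points.

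**3. If 6.5 is a single-visit SD.** Then the SD of the change is 6.5 × √(2(1 − ρ)). With no early benefit (f = 0):

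| ρ | SD of change | power, 53 per arm | power, 44.63 per arm |
|---|---|---|---|
| 0.3 | 7.69 | 0.756 | 0.681 |
| 0.4 | 7.12 | 0.817 | 0.747 |
| 0.5 | 6.50 | 0.881 | 0.820 |

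**4. Loss.**
- Spare patients: 106 − 2 × 53 = 0. The stated total, 201 = 95 + 106, adds 106 to a count that includes the 15 withdrawn, so 106 is an enrolment figure.
- Loss that still leaves 43 per arm: 106 − 86 = 20, and 20/106 = 18.9%.
- At an assumed 15/95 = 15.8%: 106 × 80/95 = 89.26 with data, or 44.63 per arm. Power is 0.820, provided that 6.5 is the SD of the quantity tested and, for the change test, f = 0.
- Over the exact 95% interval for 15/95 (9.1% to 24.7%), on the same conditions: 48.2 to 39.9 per arm, power 0.848 to 0.775.

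**5. Reference time.** Items 1 and 2 of the statistical section use 24 hours; the paired-test sentence uses 48 hours. STUDY ACTIVITIES schedules no 48-hour USSQ, so the second version cannot be computed from the planned data. Both times fall after the two-week lead-in, so choosing between them does not cure step 2.

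**The case against.** **The descriptive analyses could show a day-5 difference.** True, but they do not test it, and both numbered comparisons use 24 hours to day 5.

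**The 4 points may be meant as a difference in change.** The text allows this reading. The power calculation would then already describe the change test and lose nothing to early benefit. But the trial would be testing gain after 24 hours, which leaves out what the lead-in had achieved by then. The definitional point stands; the power losses are conditional.

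**A reader might infer that the change test is bound to fail.** The documents do not support that. The early fraction is unknown, and with none present the test keeps 0.88 at 53 per arm.

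**A reader might infer that the trial is underpowered because no loss was allowed for.** The documents do not support that either. The gap between 43 and 53 absorbs loss up to 18.9%, above the only observed rate. Nor can one see whether 53, taken from the questionnaire developers, already includes an allowance, since their inputs are not given. Calling it the data collection endpoint points the other way, but this remains a minor matter of statement.

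**The 15 withdrawals do not refute the expectation of none.** That expectation concerns leaving the assigned group and rests on familiarity with the drugs. No reasons are given for the 15, and their regimen differed. The objection stands: 15/95 is only a labelled assumption for loss.

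**Conclusion.** The concern holds on the definition of the between-arm comparison. In the 21-day regimen, the only between-arm test listed subtracts a score taken on drug, so it gives no credit for benefit reached by 24 hours, although the objective and the pre-treatment hypothesis call for it.

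The direction is certain; the size is not. If 4 points is the day-5 difference and 6.5 the SD of the change, the stated 0.80 at 53 per arm is lost once more than about a tenth of the effect is present at 24 hours, and power falls to about a third if half is.

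The conflict between 24 and 48 hours is real. The unclear meaning of 4 points and 6.5 is missing detail, not a shown error. The zero margin between 106 enrolled and 53 per arm with data is exact but minor.

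**What to change.** 1. **Main change.** Before the 21-day data are unblinded, make the first-ranked between-arm test, at two-sided 0.05, a comparison of the day-5 urinary symptom index adjusted for the pre-medication USSQ. Place the comparison of 24-hour to day-5 change after it. The order matters: with the change test first, a null result there would block the day-5 test. If 6.5 is a single-visit SD, the day-5 comparison has power 0.88 at 53 per arm and 0.82 at 44.63, before any gain from adjustment.
2. **Definitions.** Reconcile 24 and 48 hours with the USSQ schedule. Say whether 4 points and 6.5 refer to a score or a change, and state every power figure on that basis. If 6.5 is a single-visit SD, give change-score power over a range of correlations.
3. **Numbers.** State 106 as the number randomised. Give the expected number with the scores each test needs: day 5 for the first, 24 hours and day 5 for the second. STUDY ACTIVITIES says "Early termination is only relevant if the 5 day USSQ is not completed", which does not cover a missing 24-hour score. Use pooled, blinded loss from the 21-day regimen if available, since "Subjects have been enrolled on this 21-day regimen since 10/29/2014"; otherwise use 15/95, labelled as an assumption.
4. **Exclusions.** SAFETY AND MONITORING excludes patients who are stented early or have stopped medication, while the statistical section invokes intent-to-treat for withdrawals. These passages must be reconciled, because they determine who is counted.

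**Cost.** Text only: no change in enrolment, visits or questionnaires. The change test becomes secondary, and the stated number with data becomes less favourable.

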There are several studies documenting the evidence supporting the use of alpha-blockers to reduce stent discomfort, including two recent meta-analyses^{4,6}. These analyses demonstrated a significant benefit for using either tamsulosin or alfuzozin in relieving symptoms. However, only a few studies have assessed the efficacy of anticholinergic agents in this context, despite the theoretical and anecdotal benefits of this class of drugs. The available literature on anticholinergic therapy for stent symptom relief do show benefits, e.g. in one study, tolterodine ER showed symptom improvement over placebo⁷. Data on combination therapy with both agents is even more limited and show mixed results, from no advantage to modest benefits in the combination arm^{8,9}. There is also evidence that suggests tolterodine ER does not achieve maximum benefit upon initiation of the medication. Kaplan et al. found no difference in urinary symptoms between placebo and tolterodine ER at 1 week, however by week 4 of medication therapy tolterodine ER was significantly better than placebo at improving urinary symptoms.¹⁰ There is no available literature on the effect of starting tolterodine ER prior to surgery to give maximum benefit of the medication prior to placement of a ureteral stent.

We plan to design our study in a manner that will address some of the methodological weaknesses of the aforementioned studies, and use the most commonly used alpha-blocking and anticholinergic agents and dosing: tamsulosin 0.4mg PO OD and tolterodine ER 4mg PO OD, respectively.

OBJECTIVES AND HYPOTHESIS:

University of Wisconsin-Madison

Study #: 2017-0755

IRB Approval Date: 7/17/2017

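### The only between-arm test named uses the change from 24 hours to day 5, but treatment starts two weeks before the stent, so any benefit already present at 24 hours is subtracted out

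*Combined protocol and SAP*

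**What the plan says.** **The test.** In STATISTICAL ANALYSIS & POWER CALCULATIONS, item 1 looks at change within each group between 24 hours and day 5. Item 2 compares the groups by "comparing the mean intra-group score change as described in 1 (i.e., immediately post stent insertion at 24 hours compared to day 5". The methods paragraph below adds that t-"tests will be used to assess inter-group score changes", without giving another interval. The paired t-tests are within group. The only other comparison of groups is by cross tabulation and descriptive statistics.

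**The anchor.** The same paragraph describes the paired tests as a "comparison between post-op, i.e. at 48 hours, and day 5", whereas items 1 and 2 say 24 hours.

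**Treatment and questionnaire timing.** For the 21-day regimen, STUDY ACTIVITIES says: "Patients will start the study medication 2 weeks prior to their surgery date and continue for the 1 week duration of the stent". Patients "complete the USSQ at baseline prior to starting medication to serve as a baseline assessment of urinary symptoms", and further forms follow "prior to stent insertion, and again at 24 hours, 5 days after stent insertion and post stent removal". No 48-hour form is scheduled.

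**Reason for the lead-in.** BACKGROUND AND SIGNIFICANCE says that a cited study "found no difference in urinary symptoms between placebo and tolterodine ER at 1 week" but did find one by week 4. It then notes the lack of literature on "starting tolterodine ER prior to surgery to give maximum benefit of the medication prior to placement of a ureteral stent". OBJECTIVES AND HYPOTHESIS makes greater relief from the two-week lead-in a hypothesis. It also states the objective as a mean difference in the urinary symptom index, with no time point and no test.

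**The concern.** A change score measures a treatment effect cleanly when its starting value precedes treatment. Here the starting value comes after about two weeks of randomised drug. If combination therapy has already separated the arms by 24 hours, that separation enters the change score with a negative sign.

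This runs against the design. The 21-day regimen was introduced so that the drug would have time to work before the stent goes in. The closer the lead-in comes to that purpose, the less of a real day-5 benefit the test can detect. A null result could mean that combination therapy does nothing, or that it worked fully by 24 hours and stayed that way. The test cannot tell these apart. The true baseline, the pre-medication questionnaire, is collected but appears in no named test.

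**Working it through.** **Inputs from the plan** (STATISTICAL ANALYSIS & POWER CALCULATIONS): 53 per arm; difference 4 points; SD 6.5; two-sided alpha 0.05; target power 0.80.

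**Assumptions, because the documents do not give them:**
- f, the share of the day-5 benefit already present at 24 hours: 0 to 1.
- rho, the correlation between the 24-hour and day-5 scores: 0.3 to 0.7, extended to 0.9 under the objection.
- SD 6.5 applies to a single visit's score. If it is instead the SD of the change, the rho = 0.5 column applies, since 6.5 × √(2 × 0.5) = 6.5.

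**Step 1: reproduce the plan's figure.** The normal approximation gives n = 2 × [6.5 × (1.960 + 0.842) / 4]² = 41.5, so 42 per arm. The noncentral t gives 43 per arm (power 0.805), which matches the plan. At the adopted 53 per arm, a comparison that keeps the full 4 points has power 0.88.

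**Step 2: what the planned test estimates.** Let D24 and D5 be the arm differences at the two visits. The contrast is D5 − D24. With D5 = −4 and D24 = −4f, its expected value is −4(1 − f): −4, −3, −2, −1 and 0 for f = 0, 0.25, 0.5, 0.75 and 1.

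**Step 3: its precision.** The SD of the change is 6.5 × √(2(1 − rho)), which is 7.69, 6.50 and 5.03 at rho = 0.3, 0.5 and 0.7.

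**Step 4: power of the planned test** (noncentral t, 104 df, 53 per arm):

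| Share f at 24 h | Expected estimate | rho 0.3 | rho 0.5 | rho 0.7 |
|---|---|---|---|---|
| 0% | −4 | 0.76 | 0.88 | 0.98 |
| 25% | −3 | 0.51 | 0.65 | 0.86 |
| 50% | −2 | 0.26 | 0.35 | 0.53 |
| 75% | −1 | 0.10 | 0.12 | 0.17 |
| 100% | 0 | 0.05 | 0.05 | 0.05 |

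The largest share at which 53 per arm still gives 80% power is about 11% at rho 0.5 and 31% at rho 0.7. At rho 0.3 power is below 80% even at f = 0. At f = 50%, 80% power needs 234, 167 or 101 per arm at rho 0.3, 0.5 or 0.7.

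**Step 5: the alternatives at 53 per arm.** An unadjusted day-5 comparison (difference 4, SD 6.5) has power 0.88 for every f. Day-5 ANCOVA on the pre-medication score uses SD 6.5 × √(1 − r²) with 103 df. It gives 0.88, 0.89, 0.91 and 0.95 at assumed baseline correlations r of 0.1, 0.2, 0.3 and 0.5.

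**Step 6: simulation check.** In 20,000 trials per scenario (rho 0.5, r 0.3), the change test rejected in 0.884, 0.653, 0.343, 0.121 and 0.052 of trials for f = 0 to 1. The unadjusted day-5 test rejected in 0.875 to 0.880 and ANCOVA in 0.902 to 0.906.

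**The case against.** **The plan may intend more than item 2 says.** The objective is worded as a mean difference from control, the sample size rests on a two-arm t-test of 4 points, and the t-test sentence gives no interval. No analysis is labelled primary. On this reading the fault is an unspecified contrast rather than a wrong one. This softens the wording only. The objective names no time point or test, and item 2 is the one explicit between-group interval.

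**The size of the loss is unknown.** This stands. Both f and rho are assumed, and the forms are only about four days apart in the same patient, so rho could exceed 0.7. At f = 50%, power is 0.70 at rho 0.8 and 0.94 at rho 0.9. At f = 25% it is 0.96 and above 0.99. There the change test can beat the unadjusted day-5 test. At f = 75% it still fails (0.24 and 0.42), and at f = 100% no correlation helps.

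**Early benefit may be small.** The cited onset data bracket day 15 without fixing f. Pre-existing lower urinary tract symptoms are an exclusion, so there may be little to relieve before the stent. The phrase about maximum benefit comes from a sentence on gaps in the literature, so it is the lead-in's apparent purpose rather than a formal objective. All of this is fair, but it means the planned test does best when the lead-in has achieved least by 24 hours.

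**Completers will be fewer than 106.** The 7-day regimen lost 15 of 95. At that rate 53 × 80/95 ≈ 45 per arm would remain, and the day-5 test would have power 0.82. This lowers both approaches and does not change their contrast.

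**Conclusion.** The concern holds, and the plan is wrong as written on this point. The cancellation is algebra and needs no assumption: whatever arm difference exists at 24 hours is removed from the only named between-arm test. How much power is lost does depend on assumptions. At 53 per arm, SD 6.5 and rho 0.5, power falls from 0.88 with no benefit at 24 hours to 0.35 with half of it present and 0.05 with all of it. For half the benefit the range is 0.26 to 0.53 over rho 0.3 to 0.7, and higher correlations reduce the loss further. If no benefit is present at 24 hours and rho is about 0.5 or more, the test keeps at least 0.88 power.

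The 24-hour versus 48-hour conflict is a separate defect. Either time falls after the lead-in, so settling it would not cure this one. Descriptive tables by arm do not replace a test.

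**What to change.** - Name the between-arm difference in the day-5 USSQ urinary symptom index as the primary test. An unadjusted t-test is enough to remove the defect.
- Preferably use ANCOVA with the pre-medication index as covariate. The gain may be small, because the exclusion of pre-existing symptoms may leave little baseline variation.
- Analyse the 24-hour score in the same way as a secondary outcome, and keep the 24-hour to day-5 change as descriptive.
- Reconcile the 24-hour and 48-hour wording in the statistical section with the questionnaire schedule in STUDY ACTIVITIES.

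**Cost.** The pre-medication, 24-hour and day-5 forms are already scheduled, so no visits or patients are added. Enrolment on this regimen began on 10/29/2014 and this version was approved on 7/17/2017, so the change needs a dated amendment, documented as made before the 21-day data are compared by arm. The documents do not say whether that comparison has already taken place.
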